### 3.7 Coding Dictionaries

Medical history and AEs will be coded to system organ class and preferred terms using Medical Dictionary for Regulatory Activities (MedDRA) dictionary version 22.0.

Medications will be coded according to the latest version of the World Health Organization's (WHO) WHODrug Global Dictionary version prior to the database lock.

### 3.8 Toxicity and Severity Grading Scales

The toxicity grading scales (Grade 1 to 4) that will be used for safety assessment in this study are presented in Protocol EBS.AVA.210, Appendix A ([Table 12](#) and [Table 13](#)), based on the FDA Guidance for Industry: *Toxicity Grading Scale for Healthy Adult and Adolescent Volunteers Enrolled in Preventative Vaccine Clinical Trials* ([CBER, 2007](#)). The severity of AEs, vital signs, and reactogenicity events will be assessed by the PI or the designee. Selected clinical laboratory results will be graded by the central laboratory for analytes appearing in Protocol EBS.AVA.210, Table 13 and reviewed by the PI or the designee. The toxicity grading scale has specific grading options for some clinical symptoms, such as nausea/vomiting, diarrhea, headache, fatigue, and myalgia. For symptoms not appearing on the grading scale, the grading for generic “illness or clinical AE” will be used (refer to Protocol EBS.AVA.210, Table 12). For reactogenicity assessment, a Grade of 0 will be available in the e-diary to record “symptom not present”.

## 4 STATISTICAL ANALYSIS

### 4.1 General Considerations

Data summaries will be tabulated by appropriate grouping for each analysis population as specified in [Section 3.2](#). Continuous variables will be summarized by descriptive statistics including number of non-missing observations (n), mean, standard deviation (SD), median, minimum and maximum. Categorical variables will be summarized by the frequency count (n) and the percentage of participants (%) in each category. Logarithm transformation will be used when appropriate.

All clinical laboratory data and vital sign data will be reported using standard international units, if applicable. The immunogenicity response TNA NF50 is a unitless quantitative result as it is derived from ED50 divided by the reference standard of ED50.

The reporting conventions in [Appendix I](#) will be applied to all tables, listings, and figures. All derivations, statistical analyses, summaries, and listings will be generated using SAS Version 9.4 or higher (SAS Institute, Inc., Cary, North Carolina, United States).

### 4.2 Precision

Safety variables (i.e., clinical laboratory values, vital signs) including derivations thereof will be reported to the same precision as the source data. The immunogenicity response TNA NF50 will be reported with one decimal place or two significant digits (e.g., 0.032, 18.0).

All PK concentrations will be reported and analyzed with the same precision as the source data provided by the bio-analytical laboratory regardless of how many significant figures or decimals the data carry. Derived PK parameters will be rounded for reporting purposes in by-subject listings. The unrounded derived PK data will be considered the source data for the calculation of descriptive statistics and the statistical analysis. For most derived PK parameters, 3 significant digits will be used as the standard rounding procedure, with the following exceptions:

- Parameters directly derived from source data (e.g.,  $C_{max}$ ) will be reported and analyzed with the same precision as the source data.
- Parameters derived from actual elapsed sample collection times (e.g.,  $t_{max}$ ) will be reported with the same precision as the actual elapsed sampling time value of the source data. Actual elapsed time from dosing will be rounded to 2 decimal places.

Coefficient of variation will be reported to 1 decimal place. Ratios of means for pharmacokinetic parameters will be presented with two decimal places.

### 4.3 Derived Variables

In all data listings, study day(s) relative to Study Day 1 (date of randomization) will be presented. The day prior to the date of randomization is Study Day -1. There is no Study Day 0.

Study day relative to Study Day 1 will be calculated as:

- Study day = (assessment date – date of randomization) if the assessment is before the date of randomization.
- Study day = (assessment date – date of randomization + 1) if the assessment is on or after the date of randomization.

If the study day is missing due to missing dates, it will remain as missing unless specified otherwise.

### 4.4 Handling of Missing Data

Descriptive safety data summary will be based on observed cases. For imputation of completely and partially missing dates of AEs or prior and concomitant medications, if appropriate, the following conventions will be used:

- For the start date missing completely, impute the date of the first exposure to any study treatment.
- For the start date with missing day only, impute the 1st of the month unless month is same as month of the first exposure to any study treatment then impute the date of first exposure to any study treatment.
- For the start date with missing month and day, impute 1st January unless year is the same as the date of the first exposure to any study treatment then impute the date of first exposure to any study treatment.
- If the stop date is not missing and the start date is after the stop date after missing value calculation, the stop date will be used for the start date.
- For the stop date missing completely, impute date of last contact.
- For the stop date with missing day only, impute the last day of the month. If the month of the stop date is same as month of last contact then impute the date of last contact.
- For the stop date with missing month and day, impute 31st December or date of last contact, whichever is earlier.

- An AE completely missing both start and stop dates, or with the start date missing and stop date later than the first dose date of study drug, will be considered to be treatment- emergent.

Missing start/stop dates will remain as missing in the participant data listings but will be imputed to permit proper tabulation of AE and concomitant medications data.

Missing PK concentrations and missing PK sampling time will be handled as described in [Section 6.3](#) and [6.4](#).

Unless specified above, no other imputation will be made for missing data.

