**Table 1 Study Groups**

IP Group	Treatment Group	Treatment	Sample Size (N)	
1 Cipro	1A	AV7909 + ciprofloxacin (with PK assessment)	≈40	≈70
	1B	AV7909 + ciprofloxacin (without PK assessment)	30	
2 Doxy	2A	AV7909 + doxycycline (with PK assessment)	≈40	≈70
	2B	AV7909 + doxycycline (without PK assessment)	30	
3 AV7909	3	AV7909 only	70	
		TOTAL	≈210	

[figure not shown]
**Figure 1** shows the design for this study.

Ciprofloxacin (500 mg by mouth [per os] every 12 hours [q 12 hr]) will be administered to Group 1 on Days 4-9, Days 22-24 and Days 31-37, and doxycycline (100 mg by mouth [per os] every 12 hours [po q 12 hr]) will be administered to Group 2 on Days 2-9, Days 22-24, and Days 32-38.

All participants, including the 70 participants in Group 3, will receive AV7909 (0.5 mL) IM in the deltoid muscle on Days 8 and 23. For Groups 1A and 2A, the first vaccination will occur following completion of the PK sessions and after administration of the evening antibiotic (ciprofloxacin or doxycycline) dose.

An event schematic for this study is provided in **Figure 2**.

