### 2.2.4 Safety Assessments

#### 2.2.4.1 Adverse Events

AEs (including SAEs and potential AESIs) will be recorded on the AE eCRF if they occurred from the time of the first administration of any study treatment (Day 2 for Group 2, Day 4 for Groups 1 or Day 8 for Group 3) through Day 51 or EWV. From the signing of the ICF until immediately before the administration of their first study treatment, only AEs resulting from a study-related procedure will be recorded on the AE eCRF. After Day 51 and through the 12-month safety follow-up, AEs, SAEs and AEs assessed by the DSMB to be of autoimmune etiology, i.e., AESIs, will be recorded on the AE eCRF.

Safety follow-up phone contacts to collect information on AEs, SAEs and AESIs will occur at 3 months (Day 114  $\pm 14$  days), 6 months (Day 205  $\pm 14$  days), 9 months (Day 296  $\pm 14$  days), and 12 months (Day 388  $\pm 14$  days) after the last scheduled vaccination.

Refer to Protocol EBS.AVA.210, [Section 9.2](#) for reporting adverse events.

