### 8.1.3 Drug/Vaccine Related TEAEs

Adverse event causal relationship to the study treatment will be assessed by the PI or designee using terms and scales “Unrelated”, “Possibly related”, “Probably related”, and “Definitely related”. If the relationship between the AE and the study treatment is determined to be “Possibly” or “Probably” or “Definitely related”, the event will be considered as related to the IP.

To assess the causality between AEs and the study treatment ciprofloxacin, doxycycline, and AV7909, TEAEs will be tabulated with the structures as follows:

- TEAEs by SOC, PT, and Relationship to Study Vaccine.
- TEAEs by SOC, PT, and Relationship to Antibiotics.
- TEAEs onset prior to the first vaccination by SOC, PT, and relationship to ciprofloxacin or Doxycycline.

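### In Groups 1 and 2, AEs with a missing start date, or a partial one matching the month or year of first exposure, are counted as starting before vaccination whatever their true onset

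*SAP*

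**What the plan says.** SAP 4.4 gives three rules for AE start dates.

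- Completely missing: "For the start date missing completely, impute the date of the first exposure to any study treatment".
- Day missing: the 1st of the recorded month, "unless month is same as month of the first exposure to any study treatment", in which case the date of first exposure is used.
- Month and day missing: 1 January of the recorded year, "unless year is the same as the date of the first exposure to any study treatment", in which case the date of first exposure is again used.

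The rules are introduced with "if appropriate, the following conventions will be used". The section closes by saying where the imputed dates go: "Missing start/stop dates will remain as missing in the participant data listings but will be imputed to permit proper tabulation of AE" and concomitant medication data.

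SAP 8.1.3 then plans three tables of treatment-emergent AEs (TEAEs): by relationship to the vaccine, by relationship to the antibiotics, and "TEAEs onset prior to the first vaccination by SOC, PT, and relationship to ciprofloxacin or Doxycycline". In the third, the onset date decides whether an event is counted. Neither 4.4 nor 8.1.3 says how an imputed onset date is to be treated there.

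**The concern.** The imputation suits the question of whether an AE is treatment-emergent, because setting the onset to first exposure makes it so. The pre-vaccination table asks a different question: did the event begin in the few days on antibiotic alone, or after AV7909 had been given? In Groups 1 and 2 the imputed date always falls in the antibiotic-alone days, so for the affected events the answer is fixed in advance.

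At stake is the reading of one table. It is meant to show what happened under ciprofloxacin or doxycycline before any vaccine, and it could contain events that began after vaccination. The listings keep the dates missing, so they would not support the onset period that the table implies, and no footnote is planned to warn the reader.

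**Working it through.** **Inputs from the documents**

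- First treatment, SAP 2.2.4.1: "first administration of any study treatment (Day 2 for Group 2, Day 4 for Groups 1 or Day 8 for Group 3".
- Vaccination, SAP 2.2.1 below Table 1: all participants "will receive AV7909 (0.5 mL) IM in the deltoid muscle on Days 8 and 23".
- TEAE summaries run to Day 51 and to the 12-month follow-up (SAP 8.1.2), nominally Day 388.

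The plan gives no figure of its own to reproduce.

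**Assumptions not in the documents**

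Onset is equally likely on each day, visits fall on nominal days, onset on Day 8 counts as after vaccination, and no recorded stop date pulls the start date earlier.

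**1. Start date completely missing, onset to Day 51**

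The rule places 100% before vaccination. Share misplaced = (days from Day 8 to Day 51) / (days from first dose to Day 51).

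| | Days at risk | Days from Day 8 | Truly before | Misplaced |
|---|---|---|---|---|
| Group 1 | 51 − 4 + 1 = 48 | 44 | 4/48 = 8.3% | 44/48 = 91.7% |
| Group 2 | 51 − 2 + 1 = 50 | 44 | 6/50 = 12.0% | 44/50 = 88.0% |

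Groups 1A and 2A are vaccinated in the evening of Day 8. Counting that whole day as before vaccination gives 43/48 = 89.6% and 43/50 = 86.0%.

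**2. Day missing, recorded month is that of first exposure**

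Let r be the number of days from first dose to the end of a 30-day month, with r = 1 to 30 equally likely. The lag to vaccination is 8 − 4 = 4 days in Group 1 and 8 − 2 = 6 in Group 2.

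Share misplaced = Σ max(0, r − lag) / Σ r

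- Group 1: 351/465 = 75.5%
- Group 2: 300/465 = 64.5%

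**3. All AEs with only the day missing**

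The rule was applied literally to every onset day and averaged over 365 possible randomization dates. Results are the same in both groups.

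| True onset | Imputed to before Day 8 |
|---|---|
| Days 8–14 | about 87% |
| Days 23–29 | about 38% |
| Days 8–51 | about 33% |
| Days 8–388 | about 4% |

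The other two thirds or so of those to Day 51 have a later recorded month, are given the 1st of that month, and stay after vaccination. The 33% does not conflict with the 75.5% and 64.5% in step 2: those condition on the recorded month being that of first exposure.

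**4. Month and day missing**

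By the same method, about 94% of AEs with true onset on Days 8–51 are placed before vaccination, and about 48% of those with onset on Days 8–388.

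**5. Does another rule catch these events?**

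The stop-date correction in SAP 4.4 applies only when the imputed start falls after the recorded stop, so it can only move the start earlier. An AE with no start date and a stop date on Day 30 stays at Day 4 or Day 2.

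Treatment-emergent status, on the other hand, depends little on the imputation. SAP 4.4 (last convention) and SAP 8.1.1 separately classify AEs with missing start dates as treatment-emergent when both dates are missing or the stop date falls in the treatment period.

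**The case against.** The strongest reply is that little depends on this table and few events will be affected.

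- AEs are reviewed before the first vaccination on Day 8 in all four antibiotic subgroups (Protocol 8.1.2.5, 8.1.3.2, 8.1.4.5, 8.1.5.2).
- The data capture system has edit checks and queries (Protocol 11.3).
- Solicited reactions are generally not duplicated as AEs (Protocol 9.2.3), and severe diary reactions recorded as AEs have their own start-date rule (Protocol 8.3.5.1).

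This stands, and it keeps the point small. It does not make the rule right for the events that remain. The qualifier "if appropriate, the following conventions will be used" gives a programmer no instruction, and missing dates in the listings let a reader trace an event but do not correct the table.

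A second reply is that moving every unproven event to the vaccination period would reverse the error and could remove true early antibiotic events from this table. That is fair, and a separate line for undetermined events meets it.

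A reader might also infer four stronger things that the documents do not support.

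- *All incompletely dated AEs go to the first antibiotic dose.* A missing day in a later recorded month gives the 1st of that month, usually after vaccination.
- *This is the only analysis separating antibiotic from vaccine effects.* SAP 8.1.3 also tabulates by relationship to vaccine and to antibiotics, SAP 8.1.4 and 8.1.5 add relationship for serious TEAEs and AESIs, and Group 3 is a randomized vaccine-only comparator.
- *Vaccine events are re-attributed to the antibiotic.* Imputation leaves the investigator's ratings unchanged, and unrelated is one of them. SAP 3.2 groups the Safety Population by Groups 1, 2 and 3. Protocol 10.6 names antibiotic-only columns, but neither document says they are split by onset date.
- *The comparison with Group 3 is biased.* Group 3's first exposure is the first vaccination, so it has no treated pre-vaccination period to compare.

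**Conclusion.** The defect is real but narrow. In Groups 1 and 2, an AE whose start date is completely missing, or is partial and matches the month or year of first exposure, is counted as beginning before vaccination regardless of when it began. For completely missing dates the error rate is about 92% in Group 1 and 88% in Group 2, assuming uniform onset to Day 51 and nominal visit days. Another onset pattern would change these percentages but not the mechanism.

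The number of affected AEs is not in the documents and is probably small, so this is a minor clarification. It touches one safety table and no primary or secondary hypothesis test. The overall TEAE tables, the relationship tables and the e-diary reactogenicity tables do not depend on it. It is still worth correcting, because this is the only listed SAP AE table that isolates antibiotic-alone exposure by timing rather than by causality judgement, in an open-label trial.

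**What to change.** Add to SAP 8.1.3: for the table of TEAEs with onset before the first vaccination, an AE counts as pre-vaccination only if the recorded, non-imputed parts of its start or stop date establish onset before that vaccination. Two examples are a stop date earlier than the vaccination, or a recorded month that ended before it. AEs whose period cannot be established go on a separate line labelled as onset period undetermined, or are footnoted with their count by group.

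Keep the SAP 4.4 imputation for treatment-emergent status.

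The cost is one SAP sentence and a table line or footnote. No data collection, endpoint or clinical procedure changes.

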## **4.5 Diary Data Issue Handling**

### **4.5.1 Oral Temperature Data Errors**

Oral temperatures are reported by participants in the e-diary for post vaccination reactogenicity. The numeric temperature values and the associated toxicity grades with temperatures less than 90 °F or greater than 110 °F will be set to null in the analysis.

### **4.5.2 Antibiotic Dosing Data Errors**

Antibiotic self-administered at home will be reported by participants in the antibiotic e-diary. Issues related to entry of information into antibiotic e-diary will be manually reviewed by monitors and resolutions will be performed on a case-by-case basis.

## **4.6 Adjustment for Covariates**

An exploratory immunogenicity linear regression analysis will be conducted with adjustment for site, and covariates age and sex, as specified in [Section 7.2.1](#).

## **4.7 Subgroup Analysis**

For immunogenicity analysis, TNA NF50 values will be summarized by treatment group and each of the following classification variables (categories are defined in the parentheses):

- Age (18 - 30, 31 - 45)
- Sex (Male, Female)

No statistical testing will be performed for subgroup analyses.

## **4.8 Multiplicity Adjustment**

There is a single primary endpoint for each of the two antibiotics, which will be evaluated separately with independent study participants (Group 1 for ciprofloxacin, Group 2 for doxycycline). Demonstration of non- interference of steady state PK is defined separately and there is only one way to meet the primary endpoint for each antibiotic. Success is therefore defined per antibiotic only, not at the study level, and type I error is controlled for each

antibiotic. As such, multiplicity adjustment is not needed between the endpoints across the two antibiotics.

For the assessment of the steady state PK as the primary endpoint, there are two parameters,  $AUC_{0-12h}$  and  $C_{max}$ . To conclude that administration of two-dose regimen of AV7909 does not affect the steady state PK of each antibiotic, the null hypotheses should be rejected for both parameters of the corresponding antibiotic. For each parameter, the type I error rate is controlled at 5% and there is no need to adjust for multiple testing when the criteria for both parameters must be met.

Of the secondary endpoints for each antibiotic, formal hypothesis testing will only be carried out for the immunogenicity endpoints and only after the primary PK endpoint has been met for the corresponding antibiotic. If the primary PK endpoint for an antibiotic is not met, the corresponding secondary immunogenicity endpoint will be provided for information only. Non-inferiority of the secondary immunogenicity endpoint is evaluated with a one-sided alpha of 0.025. This pre-specified hierarchical order of hypotheses testing preserves the type I error rate without the need for further adjustment.

No other formal hypothesis testing will be carried out. The secondary PK endpoints (single dose antibiotic PK values) and all safety endpoints will be evaluated and reported for information only. Thus no multiplicity adjustment is needed.

## 5 STUDY POPULATION CHARACTERISTICS

### 5.1 Subject Disposition

Subject disposition will be displayed in form of tabulation and listing for all participants who signed and dated the ICF. Tabulations will include the number of participants screened, randomized, treated with any study treatment, completed the study, discontinued study treatment, and study withdrawal. Reasons for discontinuation of treatment and study withdrawal will be summarized.

The participant last study visit will be summarized by treatment group and overall for all randomized participants. The number and percentage of participants randomized by site will be provided by treatment group and overall based on the ITT population. Reasons for screen failure and reasons for exclusion from PK Population and Immunogenicity Population will be summarized.

Listings of participants excluded from the PK Population and Immunogenicity Population with reasons will be provided.

### 5.2 Protocol Deviations

Protocol deviations defined in [Section 3.1](#) will be summarized by deviation category, severity, and treatment group for each site and overall based on the ITT Population.

A listing of protocol deviations will be provided.

## 5.3 Demographics and Baseline Characteristics

### 5.3.1 Demographics

The following demographics and baseline characteristics will be summarized as continuous variables using descriptive statistics (n, mean, SD, median, minimum, and maximum) by IP/treatment group and overall for all participants in the Safety, ITT, PK, and Immunogenicity populations:

- Age (years)
- Baseline weight (kg)
- Baseline height (cm)
- Baseline BMI

The following demographics and baseline characteristics will be summarized as categorical variables with counts and percentages by IP/treatment group and overall for ITT, Safety, PK, and Immunogenicity populations:

- Age (18 – 30, 31 – 45 years)
- Sex (Female, Male)
- Race (American Indian or Alaska Native, Asian, Black or African American, Native Hawaiian or Other Pacific Islander, White, More than one Race, and Other)
- Ethnicity (Hispanic or Latino, Not Hispanic or Latino, Unknown)

Subject demographics and baseline characteristics data listing will be provided.

### 5.3.2 Medical History

Medical history will be coded to system organ class (SOC) and preferred term (PT), according to the Medical Dictionary for Regulatory Activities (MedDRA). A summary table and a listing of medical history will be provided.

## 5.4 Treatment Compliance and Exposure to Study Drugs

### 5.4.1 Compliance of Ciprofloxacin and Doxycycline

The compliance rate of ciprofloxacin and doxycycline will be computed for each participant who takes at least one dose of antibiotic as 100 times the total number of tablets taken (administered in-clinic and reported in the CRF by staff and self-administered by participants at home and reported to the e-diary) divided by the required total number of tablets that should have been taken as specified in [Figure 2](#). The compliance will be summarized as follows by appropriate treatment group:

- Number of participants taking at least 50% of protocol specified doses

- Number of participants in Group 1A taking at least 5 of 7 in-clinic ciprofloxacin doses or in Group 2A taking at least 7 of 9 in-clinic doxycycline doses prior to each PK assessment.

The subject listing of antibiotic administration will be provided.

